## 7.7 General Skin and Eye Assessments

At Visit 1, the skin will be assessed to determine eligibility – no evidence of crusted scabies, normal skin in non-infested areas. At Visits 1, and 2, the skin and eye assessments will include documentation of presence or absence of irritation, and verbal subject-reported verification that the treatment topical suspension remained on for at least 6 hours before being washed off. At Visit 3/ET, skin and eye assessments will include evidence of irritation.

Eye irritation will be rated:

- 0 no irritation
- 1 mild scleral, lid and/or conjunctiva injection
- 2 moderate scleral and or lid injection with conjunctival erythema
- 3 severe scleral and/or lid injection with conjunctival erythema and purulent drainage

## 7.8 Application of IP

The bottle will be weighed before and after application. One bottle of IP (blinded Natroba™ [spinosad] or Placebo control) contains 4-oz. of treatment product. The subject should use as much of one bottle as needed. The subject should apply a thin layer of IP from the neck down to the toes (including soles of the feet) and to the scalp (if balding) or hairline, temples, and forehead at their home on the same day it is dispensed on Visit 1. The IP should be allowed to soak into the skin or dry for 10 minutes before getting dressed. Subjects less than 12 years of age should be assisted with administration by a parent, guardian or caregiver. Showering or bathing should occur no earlier than 6 hours after treatment and no later than at least 1 hour before Visit 2.

## 7.9 Vital Signs

Height (Visit 1 only), weight, resting blood pressure (BP) and heart rate will be measured at Visits 1 and 3/ET.

## 7.10 Eligibility Review

Eligibility criteria will be reviewed at Visit 1 prior to randomization, and the subject should qualify prior to randomization.

Screen Failure: A screen failure is defined as a subject who consented but who has not been randomized. Screen failures may re-screen after review and approval by the sponsor. Re-screening may also be necessary due to timing/scheduling or washout of other treatments (except scabicides which exclude the subject) that may have occurred within the prior 4 weeks.

### **7.11 Randomization and Treatment Assignment**

Eligible subjects will be assigned to either treatment group, Natroba™ (spinosad) or Placebo control, by pre-specified un-blinded site personnel that may perform no other study specific duties. The un-blinded site personnel will assign all members from the same household to the same treatment group. The assigned subject numbers in each household will correspond to unique bottle numbers on a scheme that unblinded site personnel will assign and distribute to ensure approximately equal randomization of households to either treatment. Subjects, blinded site personnel and ParaPRO LLC will remain blinded to the treatment until after database lock. Randomization will be stratified by study site.

### **7.12 Counseling to Prevent Re-Infestation**

Subjects should be informed about methods to minimize risk of re-infestation: including avoiding skin contact with others who are infested and avoiding bedding or linens of an infested person, and simultaneous treatment of all household contacts. The following information from the Centers for Disease Control and Prevention may be used as reference:

“When a person is infested with scabies mites the first time, symptoms may not appear for up to two months after being infested. However, an infested person can transmit scabies, even if they do not have symptoms. Scabies usually is passed by direct, prolonged skin-to-skin contact with an infested person. However, a person with crusted (Norwegian) scabies can spread the infestation by brief skin-to-skin contact or by exposure to bedding, clothing, or even furniture that he/she has used.

Scabies is prevented by avoiding direct skin-to-skin contact with an infested person or with items such as clothing or bedding used by an infested person. Bedding and clothing worn or used next to the skin anytime during the 3 days before treatment should be machine washed and dried using the hot water and hot dryer cycles or be dry-cleaned. Items that cannot be dry-cleaned or laundered can be disinfested by storing in a closed plastic bag for several days to a week. Scabies mites generally do not survive more than 2 to 3 days away from human skin. Children and adults usually can return to child care, school, or work the day after treatment.”

### **7.13 Prophylactic and Rescue 5% Permethrin**

All household members that are not infested at the screening visit will be given the same blinded study treatment as household members that are infested. Subjects not cured at Day 28 will be provided with 5% Permethrin as rescue medication, which is the recommended treatment per the current standard of care, and will be directed to their primary care physician for follow-up. Subjects with an ET visit will not receive rescue medication and will be directed to their primary care physician for follow-up.

### **7.14 Study Compliance**

Study compliance will be confirmed at Visit 2.

## 8 STATISTICAL METHODS

### 8.1 Sample Size Determination

Approximately 120 “index” subjects will be enrolled (including possible 20% attrition) from 120 households and randomized 1:1 to each of Natroba™ (spinosad) and Placebo control. The index subject will be the youngest infested member of a household ( $\geq 4$  years). Referencing to the Sponsor’s Proof of Concept (POC) study (SPN-401-12) and published literature, out of 60 completed subjects, the cure rate is 70% for Natroba™ and 30% for Placebo control. Based upon a reasonable assumption of 60% cure rate for Natroba™ and 30% for placebo, a sample size of 48 study-completed “index” subjects per group will provide 80% power to declare the non-equivalency using a delta of 30% and Type I error rate of 0.05. Fisher exact test was used to calculate the sample size and the specified power in the following Table 8-1 (PASS 14; 2015, NCSS, LLC., Kaysville, Utah, USA. [www.ncss.com](http://www.ncss.com)).

**Table 8-1 SAMPLE SIZE NEEDED TO DECLARE NON-EQUIVALENCY WITH RESPECT TO THE PROPORTION OF SUBJECTS ACHIEVING COMPLETE CURE WITH A TYPE I ERROR RATE=0.05 AND SPECIFIED POWER**

| Natroba™ | Proportion in |                           | Required
Sample Size per
Group | Power |
|----------|---------------|---------------------------|--------------------------------------|-------|
|          | Placebo       | Difference vs.
Placebo |                                      |       |
| 55%      | 30%           | 25%                       | 69                                   | 80.4% |
| 60%      | 30%           | 30%                       | 48                                   | 80.0% |
| 65%      | 30%           | 35%                       | 37                                   | 80.6% |

Assuming a drop-out rate could be at most 20%, 120 subjects should guarantee at least 48 evaluable subjects for each treatment group at Day 28 assessment.

### 8.2 Randomization

This study will investigate 2 treatment groups: Natroba™ (spinosad) Topical Suspension, 0.9% or Placebo control. A randomization scheme will be used locally at each site (stratified by study site) to obtain a balanced allocation of treatments (approximately 1:1) to the households.

### **8.3 Analysis Populations**

#### **Safety Population**

The safety population will comprise all subjects who received one dose of IP. Subjects will be analyzed as treated. The safety population includes the “index” subjects along with any household members enrolled in the study. All safety analyses will utilize the safety population.

#### **Intent-to-Treat Population**

The intent-to-treat (ITT) population will comprise all subjects who were randomized regardless of whether they have post-baseline assessments. Subjects will be analyzed as randomized. This population includes the “index” subjects along with any household members enrolled in the study.

#### **Index Intent-to-Treat Population**

The “index” intent-to-treat (I-ITT) population will comprise all index subjects who were randomized. Subjects will be analyzed as randomized. The index subject will be the youngest infested member of a household ( $\geq 4$  years). This analysis population will be used for the efficacy analysis.

#### **Index Per Protocol Population**

The “index” Per Protocol (I-PP) population is a subset of the I-ITT population. Index subjects will be excluded from the I-PP population for the following reasons:

1. Protocol deviations that would be in violation with the established Inclusion or Exclusion Criteria.
2. Protocol deviations that could confound the evaluation of efficacy outcomes:
  - Scabies assessment not performed (i.e. burrows, lesions, pruritis, skin scraping).
  - Subject received the wrong treatment.
  - Discontinuation prior to acquisition of Visit 3 (Day 28) efficacy measurements.
3. Protocol deviations that are a result of subject non-compliance:
  - Missed Day 2 appointment.
  - Use of another scabicide during the study.
  - Use of prescription or OTC medicated lotions during the study.

Prior to database lock, a memo will be generated identifying any subjects that were excluded from the I-PP population along with the reason why they were excluded.

## 8.4 Missing Values

There will be no imputation for missing events and assessments in handling safety data.

If a subject has observed data for complete cure at Day 28, the observed cases (OC) will be used at Day 28. If a subject discontinues the study before Day 28, the imputation method for complete cure at Day 28 depends on the reasons of missing, i.e. informative or non-informative missing. Please refer to the SAP for more details.

For other missing efficacy data at Day 28 (e.g., clinical cure, microscopic cure, new lesions and total lesions), Last Observation Carried Forward (LOCF) imputation will be used.

Details of imputation rules for efficacy analyses and other missing data handling conventions will be included in the SAP.

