### Number of New Lesions

The number of new lesions at Day 28 will be analyzed using a negative binomial regression model to compare the treatment difference. The model will include treatment group and study site (small sites pooled) as fixed factors, and baseline total lesion count as a covariate.

This analysis will be performed on the I-ITT population.

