## **4. EFFICACY PARAMETERS**

### **4.1. Scabies Assessment**

Skin will be examined on Days 1 and 28/ET to establish positive or negative evidence of active scabies infestation.

- Scabies diagnosis – active scabies infestation confirmed by clinical signs and symptoms (evidence of burrows or presence of scabies)

inflammatory/non-inflammatory lesions and pruritus) as well as by microscopic exam of skin scraping or dermatoscopy to demonstrate the presence of mites, eggs, and/or scybala. If dermatoscopy is used it should also confirm there are burrows on the skin.

- Primary Efficacy Endpoint – complete cure is defined as demonstration of clinical cure (all signs and symptoms have completely resolved, including burrows, inflammatory/non-inflammatory lesions and pruritus) and microscopic or dermatoscopic cure with demonstration of the absence of mites, eggs, and/or scybala, and dermatoscopy negative for burrows.

Lesions should be indicated on a body diagram and/or marked with skin marker; count of existing and new lesions will be recorded.

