**6.1.5. Data Imputation Specifications**

For the safety analyses, no imputation of missing events or assessments are allowed.

For the primary efficacy endpoint (complete cure rate at Day 28), the algorithms listed below will be followed.

Any informative missing will be counted in as non-responders (failures) in the estimation of the treatment complete cure rates. Any non-informative missing will be imputed using Last Observation Carried Forward (LOCF) in the estimation of the treatment complete cure rates.

Table 2 Informative or Non-Informative Missing

Dropouts Due to			
Lack of Efficacy	Drug Related Adverse Event	Lost to Follow-up	All Other
Informative	Informative	Non-informative	Non-informative

For sensitivity analyses regarding the primary endpoint, the Observed Cases (OC), LOCF, and multiple imputation (MI) method will be used as appropriate approaches in addition to the imputation approach described for the primary efficacy analysis above. In addition, the Observed Case (OC) and LOCF methods will be used as sensitivity analyses for exploratory endpoints. Section 6.3 specifies in detail about imputation methods applicable to them.

The MI method assumes data are missing at random (MAR). The seed number is 626. The number of imputations is 5.

Step 1: Non-monotone missing data will be imputed using the fully conditional specification (FCS) method separately for each treatment arm since the response missingness could be due to treatment. A logistic regression will be used for binary data, and a discriminant function method will be used for ordinal data or classification variable with more than two levels if necessary. The following covariates will be included in the imputation model: treatment, clinical site (small sites pooled), baseline evidence of burrows and baseline score of lesions. In this step, MI procedure with FCS statement will be performed using SAS version 9.4.

Step 2: The combined imputed data sets will be analyzed using a Cochran-Mantel-Haenszel test and a logistic regression.

Step 3: The results from the analysis based on the multiply-imputed datasets will be combined by the MIANALYZE procedure in the SAS version 9.4. The p-value, estimate of odds ratio (Natroba™ vs Placebo), and the 95% confidence interval of odds ratio estimate from each multiply-imputed data set will be combined (Wilson & Hilferty, 1931; Gorja, 1992; Rubin, 1987; Li et al., 1991).

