#### Number of New Lesions

The number of new lesions at Day 28 will be analyzed using a negative binomial regression model to compare the treatment difference. The model will include treatment

group and study site (small sites pooled) as fixed factors, and baseline total lesion count as a covariate.

This analysis will be performed on the I-ITT population using LOCF approach.

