#### Total Lesion Counts

Total lesion counts will be calculated as the sum of pre-existing lesions and new lesions. The baseline captures the total lesions on the day of first study drug administration.

The change from baseline to Day 28 will be analyzed using an analysis of covariance (ANCOVA) model with treatment and study site (small sites pooled) as factors and baseline total lesion counts as a covariate.

This analysis will be performed on the I-ITT population using LOCF approach. In addition, descriptive statistics will be provided by visit based on OC data.

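### LOCF for the exploratory number of new lesions can only carry forward a Day 1 value that is zero (the best score) or undefined when a dropout has no early-termination exam

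*Protocol*

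**What the plan says.** Protocol 8.5.3.2 sets the model: "The number of new lesions at Day 28 will be analyzed using a negative binomial regression model to compare the treatment difference". Pooled site is a fixed factor and baseline total lesion count a covariate. Protocol 8.4 fills missing Day 28 values by LOCF ("new lesions and total lesions), Last Observation Carried Forward (LOCF) imputation will be used"), and SAP 6.3.2, under Number of New Lesions, agrees: "This analysis will be performed on the I-ITT population using LOCF approach".

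On timing, SAP 4.1 states: "Skin will be examined on Days 1 and 28/ET to establish positive or negative evidence of active scabies infestation". It adds that the "count of existing and new lesions will be recorded". Under Protocol 6.2 and 6.4, Day 2 covers irritation and compliance and Day 14 is a phone call, so neither yields a lesion count. SAP 6.1.2 builds the post-treatment total from pre-existing plus new lesions. For baseline, SAP 6.3.2 (Total Lesion Counts) says only: "The baseline captures the total lesions on the day of first study drug administration". No baseline number of new lesions is defined.

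SAP 6.1.5 has a separate rule for the primary endpoint: "Any informative missing will be counted in as non-responders (failures) in the estimation of the treatment complete cure rates". SAP 6.3.2 extends the primary approach to clinical and microscopic cure, but not to new lesions.

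**The concern.** LOCF needs an earlier value that means the same thing as the missing one. For new lesions there is none. The variable describes what has appeared since treatment, so before treatment it is either zero by meaning or does not exist, and neither document says which. Protocol 6.7 lists loss to follow-up as a withdrawal reason, so subjects with no post-treatment exam are foreseeable.

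The programmer would have to choose. One choice gives a dropout the best possible score. The other removes the subject from an analysis labelled I-ITT. At stake are the estimated treatment ratio for this endpoint and the consistency of the efficacy results, because the same dropout would count as not cured and as unchanged on total lesions.

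**Working it through.** **Inputs from the documents.** 120 index subjects randomised 1:1, so 60 per arm; dropout of at most 20%; 48 evaluable per arm (Protocol 8.1). Lesion exams on Day 1 and Day 28/ET only (SAP 4.1).

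**Assumed, because the documents do not give it.** How dropout divides between the arms, and how many dropouts have no ET exam. The splits below all average 20% and take no ET exams, which is the upper end.

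**1. The plan's own figure.** 60 × (1 − 0.20) = 48 per arm, as stated. At the ceiling, 60 × 0.20 = 12 per arm have no Day 28 value.

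**2. What one dropout without an ET exam receives.**

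| Endpoint | Value under the plan | Direction |
|---|---|---|
| Complete cure | Failure by rule if informative; otherwise Day 1 infestation carried forward | Not cured |
| Change in total lesions | Baseline carried forward, so change = 0 | No improvement |
| Number of new lesions | Day 1 value: zero or undefined | Best score, or no value |

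**3. If the Day 1 value is read as zero.** Let μN and μP be the true mean counts, and dN and dP the shares with no post-treatment count. With dropout unrelated to outcome, each arm mean becomes (1 − d)μ + d × 0 = (1 − d)μ. The estimated ratio is then

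(μN/μP) × (1 − dN)/(1 − dP).

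| Loss, Natroba / placebo | Subjects of 60 | Factor on the ratio |
|---|---|---|
| 20% / 20% | 12 / 12 | 0.80/0.80 = 1.00 |
| 25% / 15% | 15 / 9 | 0.75/0.85 = 0.88 |
| 30% / 10% | 18 / 6 | 0.70/0.90 = 0.78 |
| 15% / 25% | 9 / 15 | 0.85/0.75 = 1.13 |
| 10% / 30% | 6 / 18 | 0.90/0.70 = 1.29 |

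The arm that loses more subjects looks better. With equal 20% loss the ratio is unaffected, although both arm means are 20% too low.

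**4. If it is read as undefined.** LOCF imputes nothing. At the ceiling the model is fitted to 48 per arm instead of 60, and no text says so.

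**5. Are observed counts free of bias?** Not if dropouts do worse. Assume that dropouts' mean count is twice the completers' mean c, and that there is no true effect over all randomised subjects. Each full-arm mean is c(1 − d) + 2cd = c(1 + d). Setting the two arms equal gives an observed ratio of (1 + dP)/(1 + dN). Imputing zeros multiplies this by the factor in step 3.

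| Loss, Natroba / placebo | Observed counts | Zeros imputed | True ratio |
|---|---|---|---|
| 25% / 15% | 1.15/1.25 = 0.92 | 0.92 × 0.88 = 0.81 | 1.00 |
| 30% / 10% | 1.10/1.30 = 0.85 | 0.85 × 0.78 = 0.66 | 1.00 |

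In these cases observed counts are biased in the same direction as zeros, but by less than half as much.

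**The case against.** The case for leaving the plan alone has four parts.

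- **The endpoint is exploratory and a check is already planned.** SAP 6.1.5 says: "In addition, the Observed Case (OC) and LOCF methods will be used as sensitivity analyses for exploratory endpoints". Discontinuations by arm and reason are tabulated anyway. This stands and keeps the stakes low. It does not supply the missing definition: SAP 6.3.2 still names LOCF as the analysis for this model.
- **ET exams should fill the gap.** Protocol 6.7 asks for a full set of Visit 3 procedures when a subject withdraws. Where that happens there is a real post-treatment count. The rule fails only where it does not happen.
- **The harm is conditional.** The documents never say that the Day 1 value is zero. If it is treated as undefined, the result is already close to an observed-case analysis. This is correct: every bias figure in step 3 needs the zero reading, missing ET exams and unequal loss.
- **Observed counts have their own bias.** Also correct, as step 5 shows.

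A reader might infer more than the documents support. One inference is that the rule favours Natroba. The direction depends on which arm loses more subjects, and no arm-specific dropout is given. Another is a particular inflation of the false-positive rate or loss of power. The documents give no mean or dispersion for lesion counts, so no such figure can be derived from them. A third is that the primary endpoint has the same fault. It does not: the Day 1 status of an index subject is infested, so carrying it forward gives a defined and unfavourable result.

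**Conclusion.** The prescribed rule gives a wrong value or no value for index subjects with no post-treatment lesion exam. That follows from the visit schedule and the definitions alone. Its numerical effect rests on assumptions: with the value read as zero, no ET exams, 20% loss overall and dropout unrelated to outcome, the ratio is multiplied by 1.00 with equal loss, by 0.88 or 1.13 with a 25%/15% split, and by 0.78 or 1.29 with a 30%/10% split. Lower dropout or more ET exams would leave fewer subjects affected.

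This is a worthwhile correction to an exploratory analysis and nothing more. It does not touch the primary conclusion. Nor should a reader go on to infer that dropout undermines the sample size: Table 8-1 is openly labelled as for completers and reproduces (80.05% by Fisher's exact test at 48 per arm).

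**What to change.** - **Protocol 8.4:** remove new lesions from the list of endpoints imputed by LOCF.
- **SAP 6.3.2, Number of New Lesions:** replace the reference to LOCF with *on observed post-treatment counts; a Day 1 value is not carried forward*.
- **SAP 6.1.5:** apply the same limit to the LOCF sensitivity analysis for this endpoint.
- **ET counts:** state how they enter. Use Day 28 counts as the main data set and add ET counts in a sensitivity analysis, because an early ET count covers a shorter time for new lesions to appear. SAP 6.1.4 places ET data for by-visit summaries but does not settle this for the model.
- **Reporting:** give by arm the number with no post-treatment count and the number with only an ET count.
- **Total lesions:** leave LOCF unchanged. There the Day 1 value is defined and means no change.

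**Cost.** A short protocol amendment (Protocol 12.1), matching SAP text before unblinding, and little programming. Subjects without a Day 28 count, at most about 12 per arm at the 20% ceiling, leave the main model. The remaining counts are still biased if dropouts do worse, though less than with zeros.

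Because the endpoint is listed as exploratory, the requirement for FDA agreement on primary and secondary analyses (Protocol 8.5) should not apply. Protocol 3.1 and SAP 2.2 do call lesion-count improvement a key secondary endpoint. SAP 6.1.2 grades that improvement on total lesions, so it appears to be a different variable, but the sponsor should confirm this.

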## 8.5 Statistical Analyses

A statistical analysis plan (SAP), in addition to this section of the study protocol, will describe statistical methodology for analyses and data reporting. A version of the SAP will be prepared at the same time as the protocol is finalized. However, the primary and secondary efficacy endpoints and analyses on them will not be altered unless agreed upon with the FDA. SAP will be finalized before the database is unblinded.

Data collected in this study will be presented using summary tables, figures, and subject data listings. Summary tables will present data by treatment group and, if applicable, by scheduled time of data collection. Continuous variables will be summarized using descriptive statistics, presenting the number of subjects, mean, standard deviation, median, minimum, and maximum. Categorical variables will be summarized by frequencies and percentages. Figures may be used to support the presentation of certain data.

For efficacy analyses, small study sites may be pooled together. Details on the pooling algorithms are provided in Section 8.5.3.3.

All statistical tests and confidence intervals will be 2-sided at an alpha level of 0.05.

